12 DATA AND SAFETY MONITORING

Phase I studies will be reviewed at the scheduled Roswell Park Phase I meetings and the minutes are forwarded to the IRB for review.

The Roswell Park Data and Safety Monitoring Board will assess the progress of the study, the safety data, and critical efficacy endpoints. The DSMB will review the study annually and will make recommendations that include but not limited to; (a) continuation of the study, (b) modifications to the design (c) or termination of the study.

13 STATISTICAL METHODOLOGY

This is single-center, open-label, prospective Phase I/Ib clinical trial evaluating the safety, efficacy, and pharmacokinetics/pharmacodynamics of carfilzomib and standard R-ICE combination therapy in adult patients with relapsed/refractory diffuse large B-cell lymphoma. The statistical design is based on a dose-finding algorithm to determine the maximal tolerated dose (MTD) of the study regimen and an assessment of the efficacy of the treatment for patients as compared to an external standard, i.e., R-ICE historical control. All enrolled patients will receive the study drug and initiation of the treatment should take place as soon as possible following study enrollment. A maximum total of up to 21 evaluable patients will be enrolled in the Phase I of this study, and a total of 9 evaluable patients will be enrolled in the Phase Ib portion of the study. An evaluable subject is defined as a subject who meets eligibility requirements and who does not discontinue prior to end of Cycle 1 for reasons other than DLTs for Phase I or who completes at least 1 cycle of planned therapy for Phase Ib. If a subject signs

an Informed Consent and does not receive treatment, the subject will not be classified as evaluable and will be replaced. Unevaluable patients will be replaced. Analyses will be performed with a focus on estimation of specific clinically important parameters for use in the planning of larger subsequent comparative trials designed to fully assess efficacy and safety.

13.1 Sample Size Determination

13.1.1 Phase I

The actual sample size for the Phase I population depends on the unknown dose-toxicity profile of the treatment and the sample size is 21.

13.1.2 Phase Ib

The sample size calculation for the Phase Ib population is based on testing the hypotheses concerning the proportion of the population who experience an objective response (i.e., CR or PR) described above. This design requires a total of up to 30 patients in order to achieve approximately 80.1% power to detect differences of 20 percentage points (50% versus 70%).

Based on the excellent response observed in the patients treated in the Phase I portion (ORR 90%) and budget changes, the sample size for the Phase Ib portion was reduced. The phase Ib portion will include 9 additional patients. The efficacy analysis will include evaluable patients in the Phase I and Phase Ib portions combined (sample size up to 45). The sample size calculation for the efficacy analyses is based on testing the hypotheses concerning the proportion of the population who experience an objective response (i.e., CR or PR) described above. This design requires a total of up to 30 patients in order to achieve approximately 80.1% power to detect differences of 20 percentage points (50% versus 70%).

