4. METHODOLOGY

4.1. Study Design

This is an open-label, non-randomized, multicenter, dose-escalation Phase I, followed by Phase Ib expansion study of carfilzomib in combination with R-ICE regimen in relapsed/refractory DLBCL patients. Based on the results of the Phase I portion of the study, the Phase Ib dose will be at Dose Level 6. The study schema is depicted in **Figure 6**.

Figure 6. Treatment Plan Schema

Subjects will be treated on an inpatient and outpatient basis. All subjects will meet the inclusion and exclusion criteria summarized in **Section 5.1** and **Section 5.2** prior to enrollment in this study.

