13.5 Phase Ib (expansion cohort)

The objective of the Phase Ib component is examination of the efficacy and toxicity of the addition of carfilzomib to R-ICE at the MTD dose.

The primary objective of the Phase Ib component is to assess the efficacy of the study treatment arm as compared to historical control. The primary efficacy endpoint will be best overall response rate (PR+CR) within following 3 cycles of C-R-ICE therapy (as demonstrated by whole body PET-CT and dedicated CT scans following Cycle 3 of therapy).

The efficacy analysis will include patients treated in the Phase I and Phase Ib part of the study. This change in the protocol was decided based on the excellent ORR observed in the first 15 patients treated in the Phase part of the study and changes in the protocol budget.

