13.5.2 Phase Ib Decision Rules

Let π represent the proportion of the evaluable population of interest who experience an overall response within 3 weeks after completion of therapy (i.e., 3 cycles) at the carfilzomib MTD. If the response rate of less than 50% is considered unacceptable. A response rate of more than 70% is considered promising and evidence of such will deem the treatment worthy of further study. The null and alternative hypotheses corresponding to the design are

$$H_0 : \pi \leq 50\%,$$
$$H_a : \pi > 50\%.$$

A total of up to 30 evaluable patients will be accrued in the Phase I and Phase Ib portions of the study. The evaluable population is defined as patients who meet eligibility requirements and complete at least 1 cycle of therapy. Unevaluable patients will be replaced.

With this re-design, the probability is 4.8% of falsely concluding that the proportion of those who experience an overall response exceeds 50% and 80.1% is the probability of correctly concluding efficacy when the overall response rate is 70%.

In the event that the actual first stage sample size is not as planned, the adjustment of the first-stage stopping rule will be based on the approximate minimax rule proposed in Green and Dahlberg (1992): Stop the trial if the number of responses is α or less, where α is the largest value for which power properties would be maintained given the attained first-stage sample size, assuming the planned final sample size is achieved and one applies the planned final boundary. If the planned second stage sample size is not attained, the bound will be adjusted so to preserve Type I error.

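### Thirty patients cannot give the stated 80.1% power at 4.8% type I error: the exact test at 5% or less has 73.0% power, and no success boundary is written

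*Combined protocol and SAP*

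**What the plan says.** The synopsis and section 13.1.2 both give 80.1% power for 50% versus 70% with a combined total of 30 patients, made up of up to 21 from Phase I and 9 from Phase Ib. Section 13.1.2 puts it as "This design requires a total of up to 30 patients in order to achieve approximately 80.1% power". Section 13.5.2 sets H0: π ≤ 50% against Ha: π > 50% and attributes the error rates to the revised plan: "With this re-design, the probability is 4.8% of falsely concluding that the proportion of those who experience an overall response exceeds 50" per cent, with 80.1% as the probability of concluding efficacy at a true rate of 70%.

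Three further statements bear on this:

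- **Sample size.** Section 13.1.2 also describes the efficacy set as the two "portions combined (sample size up to 45" patients), which conflicts with 30.
- **Stages.** Section 13.5.2 provides for departures from a two-stage plan: "In the event that the actual first stage sample size is not as planned, the adjustment of the first-stage stopping rule" follows a published minimax approximation, and "If the planned second stage sample size is not attained, the bound will be adjusted so to preserve Type I error". No stage size, stopping number or final number of responders is given anywhere.
- **Timing and population.** Section 13.5 says of pooling Phase I with Phase Ib: "This change in the protocol was decided based on the excellent ORR observed in the first 15 patients". The hypothesis concerns response "after completion of therapy (i.e., 3 cycles) at the carfilzomib MTD", while section 4.1 says "the Phase Ib dose will be at Dose Level 6", so a pooled set includes Phase I patients from lower levels of the escalation.

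**The concern.** The 4.8% and 80.1% are presented as properties of the current 30-patient plan for the primary efficacy endpoint. If 30 patients cannot deliver them, the trial is less able to recognise its own target effect than a reader is told.

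The missing boundary matters more in practice. At 30 patients, moving the cut-off from 20 to 19 responders doubles the type I error. With no written number, the cut-off could be settled after the final data are known. The protection of a written rule is especially needed here, because the sample size and the pooling were themselves changed after responses had been seen.

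**Working it through.** **Inputs.** Null rate 50% (sections 13.5.1 and 13.5.2); alternative 70% (sections 13.1.2 and 13.5.2); n = 30 evaluable (section 13.5.2); one-sided test (section 13.5.2); unevaluable patients replaced, so no dropout allowance.

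**Step 1: try to reproduce the stated pair at n = 30.** For a rule that succeeds at r or more responders, type I error = P(X ≥ r | 30, 0.5) and power = P(X ≥ r | 30, 0.7), with X binomial.

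| r of 30 | Type I error | Power |
|---|---|---|
| 19 | 10.02% | 84.1% |
| 20 | 4.94% | 73.0% |
| 21 | 2.14% | 58.9% |
| 22 | 0.81% | 43.2% |

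No row gives 4.8% with 80.1%. The lowest cut-off with type I error at or below 5% is 20.

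**Step 2: try other methods at n = 30.** The usual normal approximation at one-sided 5% has s0 = √(0.25/30) = 0.0913 and s1 = √(0.21/30) = 0.0837, so power = Φ[(0.20 − 1.645 × 0.0913)/0.0837] = Φ(0.596) = 72.4%. Other versions give 70.7% (null variance only), 77.2% (alternative variance only), 65.4% (continuity-corrected) and 72.9% (arcsine). An exact two-sided 5% test needs 21 responders and has 58.9% power. None gives 80.1%.

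**Step 3: could an unstated two-stage rule rescue it?** No. By the Neyman–Pearson lemma, no rule based on at most 30 binary outcomes, in one stage or two, beats the randomised most powerful test on all 30.

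- At 5%, that test rejects at 20 or more, and at 19 with probability (0.0500 − 0.0494)/0.0509 = 0.012. Its power is 0.7304 + 0.012 × 0.1103 = 73.2%.
- At exactly 4.8%, its power is 72.3%.
- For 80.1% power, it must reject at 19 with probability (0.8010 − 0.7304)/0.1103 = 0.640. Type I error is then 0.0494 + 0.640 × 0.0509 = 8.2%.

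A search of actual two-stage designs with N from 20 to 30 agrees. With a futility stop only, maximum power is 73.0% at type I error of 5% or less, and 72.5% where it rounds to 4.8% or lower. The smallest type I error giving the stated power is 8.5%.

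**Step 4: try the other sample size.** At n = 45, 29 or more responders gives 3.6% and 83.6%, which is not the stated pair either.

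**Step 5: where do the figures fit?** Among futility-only two-stage designs with N from 24 to 49, two fall within 0.05 of a percentage point of both figures, and both have N = 37:

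- stop at 12 or fewer of 23, succeed at 24 or more of 37: 4.82% and 80.1%;
- stop at 18 or fewer of 31, succeed at 24 or more of 37: 4.79% and 80.1%.

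The smallest single-stage n with type I error at most 5% and power at least 80% is also 37 (24 or more: 4.94% and 80.7%). Carry-over from a larger two-stage design would explain both the numbers and the leftover stage wording. The documents do not say so, and designs with early efficacy stopping could also match, so the origin is unproven.

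**Step 6: fewer than 30 evaluable.** The total is a maximum, so smaller numbers matter:

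| n | Succeed at | Type I error | Power |
|---|---|---|---|
| 29 | 20 | 3.1% | 63.6% |
| 28 | 19 | 4.4% | 68.2% |
| 27 | 19 | 2.6% | 57.7% |
| 26 | 18 | 3.8% | 62.7% |
| 25 | 18 | 2.2% | 51.2% |

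**The case against.** The arithmetic itself is not open to dispute; the case on the other side concerns consequence and remedy.

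- **Little practical effect.** Section 13 says the analyses focus on estimation for planning later trials, and the Clopper–Pearson intervals of section 13.5.3 do not depend on the power claim. At a true response rate of 90%, 20 or more of 30 is reached with probability above 99.9%. This stands as a limit on the consequence. It does not excuse the text, because section 13.5.2 still commits to a hypothesis test with stated error rates.
- **The 70% wording.** Sections 3.2 and 13.5.2 treat 70% as the target or promising rate, yet 20/30 is 66.7%. If an observed rate of at least 70% was meant, the rule would be 21 of 30 (2.1% and 58.9%); strictly above 70% would be 22 of 30 (0.8% and 43.2%). However, section 13.5.2 defines π as a population proportion, tests it against 50% and quotes power at 70%. So 70% is the design alternative, and 20 of 30 follows from the stated hypotheses. A stricter rule would move power further from 80.1%.
- **Dose wording.** Section 4.1 names Dose Level 6 without calling it the MTD. Sections 3.2 and 13.5.2, however, place Phase Ib and its hypothesis at the MTD. Either way, the pooled set mixes dose levels.

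**Conclusion.** The concern holds. With 30 patients, 80.1% power at 4.8% type I error is unattainable under any rule. The best exact non-randomised test at 5% or less gives 73.0% power at 4.94%, about 7 points below the claim, so the false-negative risk at a true rate of 70% is 27% (100 − 73.0) instead of the 20% implied. The primary efficacy conclusion also has no numerical boundary, and the stage rules meant to adjust it have nothing to adjust.

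This rests on the plan's own rates, its one-sided hypothesis and 30 evaluable patients with independent responses at a common rate. The corrected figures are nominal: they ignore that the reduction and pooling were decided after Phase I responses were seen, and that pooled patients received different dose levels.

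**What to change.** In the synopsis and sections 13.1.2 and 13.5.2:

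1. State a single-stage exact one-sided binomial test that concludes the response rate exceeds 50% if 20 or more of 30 evaluable patients respond, with nominal type I error 4.9% and nominal power 73.0% at a true rate of 70%.
2. Say that these figures ignore the response-driven change to sample size and pooling, and the inclusion of patients treated below the Phase Ib dose, which section 13.5.2 equates with the MTD.
3. Add the boundary, type I error and power for each evaluable number below 30.
4. Delete the first-stage and second-stage paragraph, or define its sizes and bounds and restate the error rates for them.
5. Correct 45 to 30 in section 13.1.2.

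Two optional clarifications: say that the two-sided statement in section 13.5.3 covers the secondary analyses only, and report a 90% Clopper–Pearson interval beside the 95% one. At 20/30 the lower limits are 50.06% and 47.2%, so only the 90% interval agrees with the one-sided test.

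The cost is protocol and SAP wording, with no added patients and no change to enrolment or treatment. The sponsor must accept a less favourable stated power.

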Study Design	This is multi-center open-label, prospective Phase I/Ib clinical trial evaluating the safety, efficacy, and pharmacokinetics/pharmacodynamics of Carfilzomib + standard R-ICE combination therapy in adult patients with relapsed/refractory diffuse large B-cell lymphoma. The statistical design is based on a dose-finding algorithm to determine the maximal tolerated dose (MTD) of the study regimen and an assessment of the efficacy of the treatment for patients as compared to an external standard, i.e., R-ICE historical control. All enrolled patients will receive the study drug and initiation of the treatment should take place as soon as possible following study enrollment. A total of up to 30 evaluable patients will be enrolled in the Phase I/Ib component
Target Accrual and Study Duration	A maximum of 21 patients for Phase I and 9 patients for Phase Ib expansion cohort will be enrolled at Roswell Park. The number of subjects required is a function of a currently unknown dose-toxicity relationship. Accrual is expected to take up to 10 years.
Study Procedures	
Disease Evaluation: Prior to study, at time of restaging; between Cycle 2 Day 15 to Cycle 2 Day 28 following Cycle 3 but before ASCT and at the end of treatment evaluation, then every 4 months (± 2 weeks) for 1 year, then every 6 months (± 2 weeks) for 2 years, then once a year (± 2 weeks) for 2 years for a total of 5 years, then as clinically indicated. The follow up period will begin at the end of study evaluation visit for patients that became ineligible for transplant for any reason but did not meet criteria for disease progression. The follow up period for patients that go on to transplant will begin at the Day +100 bone marrow biopsy. Patients that progress at any time will be followed for survival status only on a yearly basis.
 
Adverse Events: From first dose of study drug until 30 days after receiving last dose of study drug.
 
Hematology and Chemistry: Prior to study, Day 1 of each cycle, and post treatment follow-up.
 
Performance Status: Prior to study, Day 1 of each cycle, and post treatment follow-up.
 
History and Physical Examination: Prior to study, Day 1 of each cycle, and post treatment follow-up.
 
Electrocardiogram: Prior to study

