13.5.1 Historical Control

Patients in this population defined by the eligibility criteria receive standard-of-care which consist of blood product support as needed and growth factor support with each cycle. Based on provided historical information, the overall response rate in this patient population receiving standard-of-care is 50%. It is anticipated that treatment with carfilzomib added to standard R-ICE will increase the overall response rate beyond the clinically significant rate of 70%.

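### Section 13.1.2 sizes the pooled primary efficacy set at both 45 and 30: the phase caps allow only 30, no response cut-off is printed, and neither size gives the stated 4.8% and 80.1%

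*Combined protocol and SAP*

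**What the plan says.** Section 13.1.2 explains that Phase Ib was reduced to 9 additional patients and that the two phases are now pooled for efficacy. It then gives two sizes for that pooled set:

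- "The efficacy analysis will include evaluable patients in the Phase I and Phase Ib portions combined (sample size up to 45"
- two sentences later, "This design requires a total of up to 30 patients in order to achieve approximately 80.1% power to detect differences of 20 percentage points"

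The other places agree on 30:

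- Section 13, opening paragraph: "A maximum total of up to 21 evaluable patients will be enrolled in the Phase I of this study, and a total of 9 evaluable" (the second figure is for Phase Ib).
- Section 13.5.2: "A total of up to 30 evaluable patients will be accrued in the Phase I and Phase Ib portions of the study".
- Synopsis, Study Design: "A total of up to 30 evaluable patients will be enrolled in the Phase I/Ib component". The synopsis accrual and statistical entries, and section 4.2, are consistent with this.

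Section 13.5.2 sets the null hypothesis at a response rate of 50% or less against a rate above 50%. It states a 4.8% chance of a false positive and an 80.1% chance of success at a true rate of 70%. It mentions a planned final boundary but gives no number of responses for it, and neither does any other section.

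**The concern.** The pooled set is the denominator of the primary efficacy test, and its size determines how many responses are needed to declare success. With no cut-off printed, a reader has to derive one from the sample size, and the paragraph that should supply the sample size gives two. The conflict is in the current, redesigned text: the figure of 45 directly follows the sentence that adds the 9 Phase Ib patients.

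What is at stake is whether the primary test can be carried out as written. A statistician taking 45 from 13.1.2 and one taking 30 from 13.5.2 would arrive at different cut-offs and different error rates. Neither would recover the error rates that the plan states.

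**Working it through.** **Inputs.** Null rate 50% (13.5.1: "the overall response rate in this patient population receiving standard-of-care is 50" per cent). Alternative 70% (13.5.2: "A response rate of more than 70% is considered promising and evidence of such will deem the treatment worthy of further study"). Caps of 21 and 9 evaluable patients (section 13). Stated type I error 4.8% (13.5.2) and power 80.1% (synopsis, 13.1.2, 13.5.2). Assumption: the test is one-sided at 5%, as the directional alternative and the 4.8% suggest.

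**Step 1. Can 45 arise from the stated caps?** 21 + 9 = 30, which is 15 short of 45. Reaching 45 would take 45 − 9 = 36 patients in Phase I or 45 − 21 = 24 in Phase Ib, and neither figure is stated. Replacement of unevaluable patients does not help: both the caps and the 45 count evaluable patients, and replacing someone does not raise that count.

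**Step 2. The plan's own figure at N = 30.** For a cut-off of r responses, type I error = P(X ≥ r | N, 0.5) and power = P(X ≥ r | N, 0.7), with X binomial. The cut-off is the smallest r with type I error no greater than 5%.

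For r = 20, the sum of C(30, k) over k = 20 to 30 is 53,009,102. Dividing by 2^30 = 1,073,741,824 gives 0.0494. For r = 19 the result is 0.1002, which is too high, so the cut-off is 20.

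**Step 3. Both sizes side by side.**

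| N | Cut-off | Type I error | Power at 70% |
|---|---|---|---|
| 30 | ≥ 19 | 10.0% | 84.1% |
| 30 | **≥ 20** | **4.9%** | **73.0%** |
| 45 | ≥ 28 | 6.8% | 90.1% |
| 45 | **≥ 29** | **3.6%** | **83.6%** |
| Stated in plan | none printed | 4.8% | 80.1% |

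The stated pair is not reproduced at either size. At N = 30 the power shortfall is 80.1 − 73.0 = 7.1 percentage points.

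**Step 4. Do other methods rescue N = 30?** One-sided 5% normal approximations, with three choices of variance, give power of 70.7% to 77.2%. The arcsine approximation gives 72.9%. Reading the test as two-sided at 0.05, as 13.5.3 says of all tests, gives a cut-off of 21 with upper tail 2.1% and power 58.9%. The two-sided reading at N = 45 gives a cut-off of 30, upper tail 1.8% and power 74.6%. None of these reaches 80.1%.

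**Step 5. Which size fits the stated pair?** Among single-stage designs from 28 to 49 patients, the first to reach 80.1% power within 5% is N = 37 with at least 24 responses (4.9%, 80.7%). An exact search of two-stage designs with a futility stop, for totals of 30 to 46, found a match to both stated figures only at a total of 37. One example: continue if more than 12 of the first 23 respond, succeed at 24 or more of 37 (4.8%, 80.1%). That the stated figures came from such a design is an inference; the plan does not say so.

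**The case against.** The strongest reply is that 45 is an isolated slip. Every other statement resolves to 30, including the rest of 13.1.2. The caps are counted in evaluable patients, so a set of 45 cannot be accrued without an amendment. This stands, and it sets the severity.

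It also rules out several stronger readings.

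- A reader might infer that the plan contains two contradictory success cut-offs. It contains none. The cut-off is missing, and the two sizes merely imply different ones.
- A reader might infer that the analysts could pick the more convenient denominator once responses are known. Under the 21 + 9 caps there is no 45-patient set to pick. Section 13.5.2 also says that the bound is to be adjusted to protect type I error if the second-stage size is not reached. That clause gives no stage sizes or boundary, so it cannot be applied as it stands, but it shows that the bound is meant to follow the attained number.
- A reader might apply the 20-response cut-off to 45 patients and report a very high false-positive rate. That pairs a threshold the plan never states with a sample it cannot enrol, so it says nothing about this trial.

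What the reply does not settle is the missing cut-off or the error rates. Settling on 30 leaves both open.

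**Conclusion.** The point holds as a wrong sample size, a missing decision boundary and error rates that do not match either size. The figure of 45 in 13.1.2 cannot be reconciled with the caps or with the totals elsewhere; 30 is the only size that the plan supports. At 30, the exact one-sided 5% test needs at least 20 responses, with type I error 4.9% and power 73.0%. At 45 it would need at least 29, with 3.6% and 83.6%.

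These figures rest on a single-stage exact binomial test, one-sided at 5%, with all 30 evaluable patients accrued. Because 30 is a ceiling, a smaller attained number would need its own cut-off.

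Severity is moderate. The wrong number is easy to recognise and cheap to correct, but it concerns the primary test, and removing it alone would leave the stated 80.1% power unsupported.

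**What to change.** Make three changes in one edit:

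1. In 13.1.2, change the pooled efficacy size from 45 to 30.
2. In 13.5.2, print the success cut-off for that size: at least 20 responses among 30 evaluable patients.
3. Replace 80.1% with 73.0% in the synopsis, 13.1.2 (both places) and 13.5.2, and replace 4.8% with 4.9% in 13.5.2.

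The third change is needed because printing 20 of 30 beside the old error rates would create a new visible inconsistency. The cost is a less favourable stated power; no patients or procedures are added.

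If 45 was really intended, the synopsis (accrual, design and statistical entries), 4.2, the opening of 13, 13.1.1, 13.1.2 and 13.5.2 must all be changed to match, with the cut-off, type I error and power for 45 (at least 29, 3.6%, 83.6%). That route means enrolling up to 15 more evaluable patients than the current caps allow.
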